1 STUDY OBJECTIVE

2 STUDY DESIGN

This will be a 3-center, open label study. 24 subjects will be enrolled. Target lesion will be identified on either the knees or elbows and evaluated for efficacy (TLSS) for the secondary endpoints at baseline, week 2 and week 4 (secondary). PGA will be recorded at baseline, week 2 and week 4 (primary endpoint). TLSS is expected to be a minimum score of 2 (moderate) for erythema, 2 (moderate) scaling, 2 (moderate) plaque thickness with overall score of 6. The study will consist of screening/baseline, week 2 & week 4. (3 visits). Adverse events will be recorded throughout study. Selected patient target lesions will be photographed at baseline, week 2 & week 4. Patients will be instructed to apply a 2 sec spray time per 1% BSA on plaques and instructed to wash their hands thoroughly after application.

Subjects will attend a Screening Visit/Baseline visit and if found eligible will be randomized to study treatment. Patients will be counselled on the use of the study medication and the medications will be labelled for the appropriate group as noted above. The duration of the study is 4 weeks and consists of a Screening/Baseline visit, and one (1) Follow-up Visit at Week 2 and end of treatment visit at week 4.

3 SELECTION AND WITHDRAWAL OF SUBJECTS

3.1 Inclusion Criteria

Inclusion:

i. 1. Outpatient, male or female subjects of any race, 18 years of age or higher. Female subjects of childbearing potential must have a (-)UPT result at within 7 days of the first dose of study drug and practice a reliable method of contraception throughout the study;

A female is considered of childbearing potential unless she is:

- postmenopausal > 5Y, without a uterus and/or both ovaries; or has been surgically sterile for > 6M.

Reliable methods of contraception are:

- hormonal methods or IUD in use > 90d prior to study drug administration, barrier methods plus spermicide in use > 14d prior, or vasectomized partner.

[Exception: Female subjects of CBP who are not sexually active are not required to practice a reliable method of contraception and may be enrolled at the Investigator's discretion provided they are counselled to remain sexually inactive for the duration of the study and understand the risks involved in getting pregnant during the study.

- ii. Moderate plaque type psoriasis eligible for topical therapies.
- iii. Patients with a minimum of 3% BSA to a maximum of 20% BSA & bilateral symmetric psoriatic plaques of 2 to 4 cm in diameter
- iv. Physician Global Assessment (PGA) score of 3.
- v. Able to understand study requirements and sign Informed Consent/HIPAA forms.

Exclusion:

- i. Female subjects who are pregnant, breast-feeding, or who are of childbearing potential and not practicing a reliable method of birth control, or male subjects planning a pregnancy with their spouse or partner while in the study.
- ii. History of hypercalcaemia or vitamin D toxicity.
- iii. Patients with guttate, erythrodermic, or pustular psoriasis
- iv. Serious skin condition (other than psoriasis) or uncontrolled medical condition (in the opinion of the investigator).
- v. Topical steroids, topical immunomodulators, topical vitamin D derivatives, tar, salicylic acid, anthralin or any other topical treatment for psoriasis within 2 weeks of baseline.
- vi. Use of any biologics within 3 months of baseline.
- vii. Use of other systemic psoriasis treatments (ie, oral retinoids, methotrexate, cyclosporine, or other immunomodulators) within 4 weeks of baseline.
- viii. Use of UVB or PUVA within 2 weeks of baseline.
- ix. Skin conditions (e.g. eczema) psoriasis that may interfere with evaluations of psoriasis.
- x. Known hypersensitivity to Enstilar or any of its components.
- xi. Contraindications according to Enstilar
- xii. Current drug or alcohol abuse (Investigator opinion).
- xiii. Subject unable to commit to all the assessments required by the protocol

3.3 Withdrawal of Subjects

It is the right and duty of the Investigator to discontinue the study participation of a subject when the subject's health or well-being is threatened by continuation in the study. Such subjects should be withdrawn from the study and not continued under a modified regimen. The following are circumstances that would result in the subject's discontinuation from the study:

- the subject experiences a serious adverse event rendering them unable to continue study participation;
- the subject is unable to physically or mentally tolerate the use of the test medication;
- an exclusion criterion becomes apparent at any time during the study; or
- the subject voluntarily withdraws.

In the event of premature discontinuation from the study, the Investigator should determine the primary reason for discontinuation.

If a subject withdraws for any reason, the subject will be replaced.

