4 TREATMENT OF SUBJECTS AND FOLLOW-UP

4.1 Study Procedures

4.1.1 Assessment Schedule

Procedures/Non-Procedure Description	Screening and Baseline	Week 2	Week 4
Informed Consent	Х		
Medical History and Demographics	Х		
Inclusion/Exclusion Criteria	Х		
Initial Prior/Concurrent Medications	X		
Concurrent Medications subsequent visit	X	Х	X
Vital Signs (includes height/weight for initial visit only)	Х	Х	X
Complete Physical Examination	X		Х
TLSS scoring	X	Х	X
Pregnancy Test (female subject of childbearing potential only)	X		Х
Photography of Target Lesion (investigator will supply all photographic equipment and background) *	X	X	X
Adverse event assessment and reporting if applicable	Х	Х	X
Clinical severity/efficacy assessments by investigator (BSA, PGA)	X	Х	X
Pharmacy Dispense/Drug Accountability	Х	Х	Х

^{*}At select sites only

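### Section 3.3 removes subjects from the study, not only from the foam, for intolerance or threatened well-being, and no exit PGA, BSA or TLSS is planned

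*Combined protocol and SAP*

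**What the plan says.** Section 3.3 tells the investigator to end a subject's participation when staying in the study threatens health or well-being, and adds: "Such subjects should be withdrawn from the study and not continued under a modified regimen". Among the circumstances leading to discontinuation from the study it lists that "the subject is unable to physically or mentally tolerate the use of the test medication". Two further sentences deal with the exit: "In the event of premature discontinuation from the study, the Investigator should determine the primary reason for discontinuation" and "If a subject withdraws for any reason, the subject will be replaced".

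Section 2 states that "PGA will be recorded at baseline, week 2 and week 4 (primary endpoint"), and it fixes the end-of-treatment visit at week 4. The table in section 4.1.1 marks TLSS and the row "Clinical severity/efficacy assessments by investigator (BSA, PGA") at baseline, week 2 and week 4. It has no early-termination column, and the visit lists in section 4.1 add none.

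Section 7.2 defines the intent-to-treat population as everyone enrolled who was given study medication. It plans descriptive statistics and mean scores, and it gives no rule for missing scores.

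**The concern.** The analysis population and the data collection do not match. A treated subject who cannot tolerate the foam counts in the population, but the plan stops scoring that subject at exit. Replacement brings the number of completers back up and recovers none of the missing outcomes.

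The loss is also selective, because the unscored subjects are those who did badly with the drug as a product to use. A week-4 mean presented as the result for all treated subjects would then rest mainly on those who tolerated it. In a pilot whose main output is a description of week-4 scores, readers should be able to see that gap.

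**Working it through.** The plan has no figure of its own to reproduce here. It states no dropout rate, SD or effect size, and section 7.1 says the sample size is not formally justified. The check is therefore a reading of the sections together, followed by a small illustration.

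**What is scored, by time of exit**

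| Exit for intolerance or threatened well-being | Baseline | Week 2 | Week 4 | In intent-to-treat population (7.2)? |
|---|---|---|---|---|
| Before week 2 | yes | no | no | yes |
| Between week 2 and week 4 | yes | yes | no | yes |

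Eligibility requires a "Physician Global Assessment (PGA) score of 3", so the baseline PGA is 3 for everyone. A subject who leaves before week 2 thus contributes nothing on PGA response.

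Section 2 can be read as making PGA primary at all three visits or at week 4 only. On the first reading, a subject who leaves after week 2 still gives a week-2 primary score and only the week-4 part is lost.

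**Share of week-4 scores unobserved**

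Inputs: N completers after replacement, taken as 24 (section 2) or 28 (section 7.1); k treated subjects who leave for these reasons and are replaced. That 24 or 28 counts completers is an assumption.

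Share = k/(N + k). For k = 1:

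- N = 24: 1/25 = 4.0%
- N = 28: 1/29 = 3.4%

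If 24 or 28 were instead the total treated, one such subject would be 1/24 = 4.2% or 1/28 = 3.6%, which is practically the same.

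**How far one missing score could move the week-4 mean PGA**

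Assumption: the missing score lies somewhere in a 3-point range, for example 0 to 3 or 1 to 4. The span of the mean is 3k/(N + k):

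- N = 24: 3/25 = 0.12 points
- N = 28: 3/29 = 0.10 points

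With the whole 0-to-5 scale allowed, the spans are 5/25 = 0.20 and 5/29 = 0.17. All of these are distances between the two extremes, not estimates of bias.

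**Scale against sampling error**

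Full 95% interval width for a mean of 24 scores = 2 × t(0.975, 23) × SD/√24, with t = 2.069 and SD assumed:

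- SD 0.8: 2 × 2.069 × 0.8/4.899 = 0.68 points
- SD 1.0: 2 × 2.069 × 1.0/4.899 = 0.84 points

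The span from one missing subject is well inside that width.

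**The case against.** The best defence is that this is an open-label, exploratory pilot with no comparator described, and that much is already in place. The intent-to-treat definition keeps withdrawn subjects in the population, so replacement does not delete them. Week-2 scores survive for anyone who leaves after that visit. The reason for leaving is determined. The bar on a modified regimen concerns dosing, and nothing in section 3.3 forbids scoring a subject at exit. All of this stands, and it limits the point to a modest one. It does not fill the gap: sites are not told to score a subject who leaves, and the visit in section 4.1.3 is tied to week 4, so three centers may act differently.

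Four stronger readings are tempting, and the documents do not support them:

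- *Several subjects will be lost.* Five such subjects with 24 completers would mean 5/29 = 17.2% unobserved and a span of 15/29 = 0.52 points. Nothing in the documents supports that count, and zero is just as compatible with them. Even that span is below the interval widths above.
- *The results are biased in a known direction.* Nothing in the documents links intolerance of the foam to a better or worse PGA. The loss is selective, but its direction is unknown.
- *Every subject who stops must be followed off drug, and those scores belong in the main summary.* With no randomised comparison to protect, that is a choice of estimand. Off-drug scores, possibly after other therapy, say less about the foam and could blur the on-treatment description.
- *All exits can be reduced to stopping the drug or withdrawing consent.* Section 3.3 also covers the case where remaining in the study is itself the threat. Such a subject should not be asked back for visits.

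**Conclusion.** The gap is real and probably small. Under sections 3.3 and 4.1, treated subjects who leave for intolerance or threatened well-being have no week-4 PGA, BSA or TLSS, and no post-baseline scores if they leave before week 2, although section 7.2 counts them. The week-4 summaries therefore describe mainly subjects who tolerated the foam.

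The size, about 3% to 4% of week-4 scores per such subject, rests on 24 or 28 completers after replacement. The number of such subjects is unknown. The discrepancy between 24 and 28 is a separate matter and does not change the conclusion.

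The finding is limited to these two withdrawal rules. It makes no claim about consent withdrawal, serious events or late-found exclusion criteria. Nor does it cover subjects who stop because control is achieved; the patient instructions allow that and are not stated to end participation. The change is worth making because it is cheap, not because the study is at risk.

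**What to change.** **Sections 3.3 and 4.1.1.** Add an early-termination assessment at the stopping visit for any treated subject who stops early and agrees. It should include PGA, BSA, TLSS and the other week-4 procedures. The section 4.1.3 list omits the row "Pregnancy Test (female subject of childbearing potential only"), which section 4.1.1 marks at week 4, so name the test explicitly where it applies.

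Keep the investigator's power and duty to end participation altogether when continuing in the study threatens the subject. Subjects who stop only the foam for intolerance and still consent may be invited to the remaining scheduled visits.

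**Section 7.2.** State three rules:

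1. Exit scores are used as last observed values in a flagged sensitivity summary and are not treated as true week-4 scores.
2. Any week-4 scores taken off drug are shown separately from on-treatment scores.
3. The number of treated subjects without a week-4 score is reported by reason.

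**Cost.** A short amendment to three sections, using existing staff and procedures for the few subjects concerned. The downside is a handful of off-schedule or off-drug scores that need flagging and say less about the foam itself.

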4 TREATMENT OF SUBJECTS AND FOLLOW-UP

4.1 Study Procedures

4.1.1 Assessment Schedule

Procedures/Non-Procedure Description	Screening and Baseline	Week 2	Week 4
Informed Consent	Х		
Medical History and Demographics	Х		
Inclusion/Exclusion Criteria	Х		
Initial Prior/Concurrent Medications	X		
Concurrent Medications subsequent visit	X	Х	X
Vital Signs (includes height/weight for initial visit only)	Х	Х	X
Complete Physical Examination	X		Х
TLSS scoring	X	Х	X
Pregnancy Test (female subject of childbearing potential only)	X		Х
Photography of Target Lesion (investigator will supply all photographic equipment and background) *	X	X	X
Adverse event assessment and reporting if applicable	Х	Х	X
Clinical severity/efficacy assessments by investigator (BSA, PGA)	X	Х	X
Pharmacy Dispense/Drug Accountability	Х	Х	Х

^{*}At select sites only

4.1.2 Screening Visit/ Baseline Visit

- Informed Consent/HIPAA
- Urine Pregnancy Test (if applicable)
- Subject Demographics/Medical History
- Concomitant Medication/Treatment
- Inclusion/Exclusion Criteria
- Assessments

- BSA (Affected Body Surface Area)
- PGA
- Identification of target lesion
- Photography of target lesion at select sites only
- TLSS
- Physical Exam
- Vital Signs / Height & Weight
- Drug dispensation
- Adverse events
- Cutaneous adverse events

Week 2

- Concomitant Medication/Treatment
- Assessments
 - BSA (Affected Body Surface Area)
 - PGA
 - Photography of target lesion at select sites only
 - TLSS
- Vital Signs
- Drug dispensation
- Adverse events
- Cutaneous adverse events

4.1.3 Week 4/End of treatment

- Concomitant Medication/Treatment
- Assessments
 - BSA (Affected Body Surface Area)
 - PGA
 - Photography of target lesion at select sites only
 - TLSS
- Physical Exam
- Vital Signs
- Drug dispensation / collection
- Adverse events
- Cutaneous adverse events

4.2 Study Treatment

4.2.1 Details of Study Treatment

Enstilar® Foam is a white to off-white opalescent liquid in a pressurized aluminum spray can with a continuous valve and actuator. At administration the product is a white to off-white foam after evaporation of the propellants. Each gram of Enstilar® Foam contains 52.2 mcg calcipotriene

hydrate (equivalent to 50 mcg of calcipotriene) and 0.643 mg of betamethasone dipropionate (equivalent to 0.5 mg of betamethasone).

Enstilar® Foam contains calcipotriene hydrate and betamethasone dipropionate. It is intended for topical use only. Calcipotriene hydrate is a synthetic vitamin D3 analog. Chemically, calcipotriene hydrate is 9.10-secochola-5.7.10(19),22-tetraene-1,3,24-triol,24-cyclo-propylmonohydrate, (1a,3ß,5Z,7E,22E,24S) with the empirical formula C27H40O3,H20, a molecular weight of 430.6, Calcipotriene hydrate is a white to almost white, crystalline compound. Betamethasone dipropionate is a synthetic corticosteroid. Betamethasone dipropionate has the chemical name pregna-1,4-diene-3,20-dione-9-fluoro-11-hydroxy-16-methyl-17,21-bis(1 oxypropoxy)-(11β,16β), with the empirical formula C28H37FO7, a molecular weight of 504.6, a: Betamethasone dipropionate is a white to almost white crystalline powder. Enstilar® Foam is a white to off-white opalescent liquid in a pressurized aluminum spray can with a continuous valve and actuator. The propellants used in Enstilar® Foam are dimethyl ether and butane. At administration the product is a white to off-white foam after evaporation of the propellants. Each gram of Enstilar® Foam contains 52.2 mcg calcipotriene hydrate (equivalent to 50 mcg of calcipotriene) and 0.643 mg of betamethasone dipropionate (equivalent to 0.5 mg of betamethasone) in a base of white petrolatum, PPG-11 stearyl ether, mineral oil, all-rac-alphatocopherol, and butylhydroxytoluene.

Dispensation and Dosage Schedule

A 4-week supply of study medication will be dispensed at baseline and applied daily from weeks 0 to week 4. Subjects will be instructed to apply study medication once per day per supplement II.

4.2.2 Treatment Assignment

All subjects who have signed an ICF will receive a 2-digit subject number, starting at 01. This subject number will be used to identify the subject throughout the study. When subjects qualify for the study, they will be randomized.

Blinding

Study treatments will be provided to subjects in an open-label manner (the identity of the study treatment will be known by all parties.)

4.2.4 Supplies and Accountability

The pharmacist will inventory and acknowledge receipt of all shipments of study medication. All study medication must be kept in a locked area with access restricted to designated study personnel. The study medication must be stored in accordance with the instructions provided with the shipment. The pharmacist will also keep accurate records of the quantities of study medication dispensed and returned by each subject.

4.2.5 Treatment Compliance

Subject compliance to study treatment regimen will be assessed at each visit; study personnel will ask each subject whether they missed any applications of study medication since the previous visit.

4.3 Concomitant Medication/Treatment

Subjects must comply with the restrictions based on prohibited medications and treatments as detailed in the exclusion criteria. Other necessary therapies that will not interfere with the response

to treatment may be provided at the discretion of the Investigator. The use of any concurrent medication, prescription or over-the-counter drug, is to be recorded in the source document along with the reason the medication was taken.

5 ASSESSMENTS OF EFFICACY

5.1 Affected Body Surface Area Assessment (BSA)

The area of body affected by psoriasis will be estimated as a percentage of the subjects total body surface area. As means to standardize measurements, the area of the subject's palm will be considered as 1% of total BSA.

5.2 Physician Global Assessment (PGA) – see attached table
The Investigator will grade the current severity of psoriasis as per PGA

6 ASSESSMENTS OF SAFETY

6.1 Safety Assessments

Throughout the study, subjects will be monitored for signs and symptoms of adverse events. All adverse events and con meds will be recorded throughout study. An *adverse event* is any pathological or unintended change in the structure, function or chemistry of the body that occurs during the study, irrespective of causality, including any illness, injury, toxicity, sensitivity, or sudden death. The condition must either not be present pre-study or must worsen in either intensity or frequency during the study. A *serious adverse event* is any untoward medical occurrence, that, at any dose:

- results in death;
- is life-threatening;
- requires in-patient hospitalization or prolongation of existing hospitalization;
- results in persistent or significant disability/incapacity;
- is a congenital anomaly/birth defect; or
- is an important medical event.

[figure not shown]
An unexpected adverse event is any treatment-related adverse event, which is not identified in nature, severity, or frequency in current literature on the test product.

6.2.2 Adverse Event Reporting

All adverse events must be recorded by the Investigator into the CRF. The Investigator will be required to describe the adverse event, onset and stop date, severity, the course of action taken, i any, as well as any pertinent data necessary to allow a complete evaluation of the adverse event For serious adverse events (SAE), an additional report (SAE report) must be completed.

6.2.3 Follow-up and Final Reports

Subjects who have had a serious adverse event must be followed clinically until all parameters including laboratory values (if applicable), have either returned to normal or are otherwise explained If death was the outcome of the event on the initial SAE Report, a Follow-up/Final Report, including autopsy report, when performed, must be completed.

7 STATISTICS

7.1 Sample Size Justification

This is a pilot study and a formal justification for the sample size is not provided. N = 28

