7.2 Analyses

Statistical analyses will be conducted on an intent-to-treat population that includes all subjects who were enrolled and received study medication. Due to small sample size and exploratory nature of the study, descriptive statistics will be performed using SAS. Any additional statistical analyses will be performed as appropriate and detailed in the final report. All statistical tests will be two-sided and interpreted at a 5% significance level. Descriptive statistics (i.e., mean, standard deviation, etc.) will be provided for all continuous variables and frequencies for all categorical variables collected in this study. Summary tables will be used to present patient population characteristics at Baseline; data from the study questionnaires will be included. Analyses of study treatment will be performed using an ANCOVA technique with the Baseline value as the covariate provided the necessary assumptions for parametric tests are satisfied. The Wilcoxon Rank-Sum test will be used if the necessary assumptions for parametric tests are not satisfied. Mean scores will also be analyzed. Safety analyses will be performed in terms of incidence and severity of local tolerance signs and symptoms and adverse and/or unexpected events.

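### Section 2 sets enrolment at 24 subjects, section 7.1 gives N = 28, and nothing in the document reconciles the two

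*Combined protocol and SAP*

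**What the plan says.** Section 2 (Study Design) states: "This will be a 3-center, open label study. 24 subjects will be enrolled". Section 7.1 (Sample Size Justification) consists of this: "This is a pilot study and a formal justification for the sample size is not provided. N = 28".

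Two other provisions affect the count:

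- Section 3.3 (Withdrawal of Subjects): "If a subject withdraws for any reason, the subject will be replaced". It gives no expected number of withdrawals and no upper limit on replacements.
- Section 7.2 (Analyses): "Statistical analyses will be conducted on an intent-to-treat population that includes all subjects who were enrolled and received study medication".

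On method, section 7.2 says: "Due to small sample size and exploratory nature of the study, descriptive statistics will be performed using SAS". It plans means and standard deviations for continuous variables and "frequencies for all categorical variables collected in this study". It also names ANCOVA, the Wilcoxon rank-sum test and two-sided testing at 5%. Section 2 makes the PGA the primary endpoint.

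**The concern.** The document gives two numbers for one basic design quantity. Section 2 ties its number to enrolment. Section 7.1 gives a bare N that could mean subjects enrolled, treated or completing week 4. A site working from section 2 would regard the study as full at 24, while one working from section 7.1 would continue to 28.

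The final report is affected too. Frequencies and means, including those for the PGA, will be computed on whoever was enrolled and treated. Without one planned N, a reader cannot tell whether the achieved number is under-enrolment, over-enrolment or completion as planned.

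**Working it through.** **Inputs**

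- Enrolment: 24 (section 2).
- N: 28, with no formal justification (section 7.1).
- Withdrawals: all replaced, with no rate and no cap (section 3.3).
- Analysis set: all enrolled subjects who received study medication (section 7.2).

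The plan has no calculation to reproduce. It states no effect size, SD, response rate, power or dropout rate. The check is whether anything in the document leads from 24 to 28.

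**Size of the gap.** 28 − 24 = 4 subjects. 4/24 = 16.7%, and 4/28 = 14.3%. This is too large to be rounding.

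**Could 28 be 24 plus a dropout allowance?** The usual inflation is 24/(1 − d), rounded up. The document gives no d, so a range is assumed:

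| Assumed d | 24/(1 − d), rounded up |
|---|---|
| 5% | 26 |
| 10% | 27 |
| 12% | 28 |
| 14% | 28 |
| 15% | 29 |
| 20% | 30 |

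The exact solution is d = 1 − 24/28 = 14.3%. An allowance of about 12% to 14% would give 28, but no section states one. Section 2 also attaches the smaller number to enrolment, which is the reverse of what an inflated enrolment target would look like.

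**Could 28 be 24 plus replacements?** Suppose 24 subjects are treated first and each treated withdrawal is replaced by a treated subject. Both remain in the section 7.2 population, so the analysed number is 24 + w, where w is the number of treated withdrawals. This equals 28 only when w = 4. The document does not state that value or present 28 as such a total.

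**What the difference does to the planned summaries**

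- One subject's weight in a frequency: 1/24 = 4.2 percentage points; 1/28 = 3.6 percentage points.
- As a gauge of precision (the plan does not itself call for confidence intervals), the 95% half-width for a mean in SD units is t(0.975, n − 1)/√n. This is 0.4223 at n = 24 and 0.3878 at n = 28. The ratio is 0.4223/0.3878 = 1.089, so the interval is 8.9% wider at 24.
- For a proportion at the worst case p = 0.5, the half-width 1.96 × √(0.25/n) is 20.0 percentage points at n = 24 and 18.5 at n = 28.

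**The case against.** The strongest reply is that little depends on the number. Section 7.1 disclaims any formal justification, so no power, error-rate or precision statement rests on either figure. The denominator of the final report is set by the section 7.2 rule, whatever N was planned. Because section 3.3 replaces withdrawals without a cap, the analysed number could exceed the target even if both sections agreed. Some pages were also removed from the text available for review and could mention the number.

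Much of this is fair. The precision effect is small, and uncertainty about the analysed number comes partly from sections 3.3 and 7.2 and would outlast a simple correction of one figure. None of it removes the contradiction. Disclaiming a justification excuses the missing calculation; it does not excuse two different numbers. Section 7.2 defines who is analysed once enrolment ends, but does not tell the sites when enrolment ends. A reconciling remark on a removed page would still leave sections 2 and 7.1 in conflict as they stand.

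**Conclusion.** The concern holds. The two figures differ by 4 subjects, 28 being 16.7% more than 24, and the available text does not show which is intended. The main consequence is an unclear enrolment target for three centres; the secondary one is the lack of a single planned N against which to read the report. It should be fixed, but its inferential weight is limited: no power or precision claim is made, so none is invalidated. The conclusion rests only on the two sentences as written and on the absence of any stated dropout rate, replacement cap or enrolled-versus-completer label. The dropout rates and the value of w tried above are assumptions used to test possible explanations, and the verdict does not depend on them.

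**What to change.** The sponsor should confirm the intended number.

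- If it is 24, change section 7.1 to N = 24.
- If it is 28, change section 2 to 28 subjects.
- If both figures are meant and count different things, label each one in both sections.

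Use the same wording in sections 2 and 7.1, for example: *N = [confirmed number] subjects [enrolled / treated / completing week 4]*. In section 3.3 add: *Replacement subjects [are counted within / are in addition to] this number.* Optionally, make the existing rule in section 7.2 explicit: *All treated subjects, including those who withdraw and their replacements, remain in the analysis population.* The replacement rule itself does not change.

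The cost is a few lines of text, with no added visits or procedures. Confirming 24 as the enrolment number adds no patients; confirming 28 adds 4 to what section 2 states. If the confirmed number is defined as completers, replacements could take enrolment above it. Section 3.3 already allows replacements, but the total should then be described that way.
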